## **6.2. Secondary Endpoints-Safety**

### **6.2.1. I-V Interwave Latency on BAEP**

- Endpoint: Change from baseline in I-V interwave latency on BAEP at a stimulus intensity of 80dB at Months 6, 9E, and 15E.
- Population: Safety.
- Statistical Method: Linear mixed-effects model in [Section 5.2](#), which includes all the post-baseline measurements through Month 6, will be used. The estimated means, with standard errors and 95% confidence intervals for each treatment group based on the model will be presented. Descriptive statistics will also be provided based on the observed data. Descriptive statistics will be presented for data in the active therapy extension phase. Data from right side and left side will be summarized separately.

### **6.2.2. Percentage of IENF with Axonal Swellings in Skin Punch Biopsies**

- Endpoint: Change from baseline in the percentage of IENF with axonal swellings in skin punch biopsies at Month 9/EOP (End of placebo-controlled phase/ beginning of active therapy extension phase) and Month 15E.
- Population: Safety.
- Statistical Method: Descriptive statistics for continuous variables.

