4. STUDY DESIGN

4.1. Overall Design

Study B7981037 is a Phase 2a, randomized, double-blind, parallel group, placebo-controlled safety study designed to evaluate the safety and tolerability of PF-06651600, including the assessment of BAEP and IENF, in adults with $\geq 25\%$ scalp hair loss due to AA.

Approximately 60 adults 18 to 50 years of age will be randomized 1:1 to receive either PF-06651600 or placebo. If there are issues related to the integrity of some peripheral nerve punch biopsy samples, up to an additional 20 participants may be added at the discretion of the Sponsor to ensure adequate numbers of participants with interpretable biopsies.

Treatment Period 1 (TP1) and Treatment Period 2 (TP2):

The total duration of participation in the study for TP1 and TP2 will be approximately 26 months.

This includes up to a 5-week screening period, a 9-month placebo-controlled treatment phase, a 15-month active therapy extension phase, and a 4-week follow-up period [for participants not continuing to TP3 or discontinuation of study intervention (see Schema Section 1.2)]. Screening will occur within 35 days prior to Day 1 of the study to confirm that selection criteria for the study are met. At Month 9, the placebo-controlled phase will end, and all participants may enter the active therapy extension phase of the study and receive PF-06651600. For any participant discontinued for a neurological or auditory adverse event, the participant will be evaluated again at 6 months after discontinuation; the maximum duration of participation in the study for such participants could be approximately 32 months if the event occurred at the last visit.

At Month 6, any participant with a baseline overall SALT score ≤ 75 will have the option to enter the active therapy extension phase if their overall SALT score at Month 6 has increased from baseline by ≥ 25 points. Those participants who enter the active therapy extension phase at Month 6 are to complete at that visit all the Month 6 (Visit 5) assessments and then follow the schedule of visits in the active therapy extension phase starting with Month 3E skipping the Month 9 (Visit 6).

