## Sample Size Determination

Approximately 60 adults 18 to 50 years of age will be randomized in a 1:1 allocation ratio to either the PF-06651600 200 mg QD/50 mg QD dose group or the placebo group.

For the primary safety endpoint, change from baseline in I-V interwave latency on BAEP at Month 9, the published standard deviations for I-V interwave latency on BAEP range from 0.1 to 0.3 ms. Assuming a standard deviation of 0.2 ms, and assuming the standard deviation of change from baseline is similar to the standard deviation of actual score, the half-width of 95% confidence interval for the group will be 0.07 ms for 30 participants per group.

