##### 5.2. General Methods

In the placebo-controlled period, the following continuous endpoints: (change from baseline in I-V interwave latency on BAEP, change from baseline in amplitude of wave V, and change from baseline in overall and AA SALT score, will be analyzed using the linear mixed -effects model with baseline, treatment group, visit, and treatment group by visit interaction as fixed effects, with an unstructured covariance matrix assumption, if there are convergence issues, a compound symmetry matrix will be used. The Kenward-Roger degrees of freedom approximation will be used. For participants who switch to the active therapy extension phase at Month 6, only their data through Month 6 will be included in the analysis of the placebo-controlled period. Descriptive statistics based on observed data will also be provided. For TP2 and TP3, descriptive statistics will be presented.

For the binary endpoint PGI-C response, in the placebo-controlled phase, number and percentage of responders with 95% confidence interval (based on Clopper-Pearson method) by treatment group, and treatment difference with 95% confidence intervals (based on Chan and Zhang's exact method) will be presented. Participants who discontinue from the study for any reason or who switch to active therapy extension phase before Month 9 will be considered as non-responders. Number and percentage based on observed data will also be provided. For TP2 and TP3, number and percentage of responders with 95% confidence interval (based on Clopper-Pearson method) will be presented based on observed data.

For all other data, descriptive summary statistics such as number and percentage will be presented for binary variables, and number, mean, standard deviation (or standard error of the mean), median, minimum, and maximum will be presented for continuous variables.

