#### **6.2.5. Absence of Wave V on BAEP**

- **Summary:** Proportion of subjects with an absence of wave V on BAEP at stimulus intensities ranging from 80dB to 40dB at Months 6, 9, 9E, and 15E.
- **Population:** Safety.
- **Statistical Method:** Descriptive statistics with number and percentage of subjects with the events only. Data from right side and left side will be summarized separately.

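### No confidence interval, baseline covariate or between-arm estimate is planned for the two skin-biopsy endpoints or for absence of wave V

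*SAP*

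**What the plan says.** - **Axonal swellings (SAP 6.2.2):** "Statistical Method: Descriptive statistics for continuous variables", applied to change from the Day 1 biopsy at Month 9/EOP and Month 15E.
- **IENFD (SAP 6.2.3):** the same method, plus a descriptive summary normalised by age and gender.
- **What descriptive means (SAP 5.2):** "number, mean, standard deviation (or standard error of the mean), median, minimum, and maximum will be presented for continuous variables". No interval is on this list.
- **Absence of wave V (SAP 6.2.5):** "Descriptive statistics with number and percentage of subjects with the events only", by ear, at intensities from 80 to 40 dB.
- **Protocol 9.4.3** agrees on all three endpoints.
- **Other endpoints get more.** I-V latency and wave V amplitude have a mixed model with baseline as a covariate and 95% intervals per arm (SAP 5.2, 6.1, 6.2.1, 6.2.4). SALT also has a mean difference with a 95% interval (SAP 6.3.1). PGI-C has Clopper-Pearson intervals per arm and a Chan-Zhang interval for the difference (SAP 6.3.2).
- **Biopsy numbers (Protocol 4.1):** if sample integrity is a problem, "up to an additional 20 participants may be added at the discretion of the Sponsor to ensure adequate numbers of participants with interpretable biopsies".

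**The concern.** The protocol's rationale (Sections 1.1 and 2.1) is to find out whether the dog findings matter in people. In the second nine-month dog study (Protocol 2.2.1), the axonal dystrophy that helped set the no-effect level appeared from 20 mg/kg/day, a 12-fold exposure multiple of the 50 mg dose. BAEP deficits appeared only at 40 mg/kg/day, a 29-fold multiple. The biopsy endpoints therefore look for the change seen at the lower exposure, and intervals on BAEP latency or amplitude do not stand in for them.

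In a study with no hypothesis test, the estimate and its interval are the inferential result. For these three endpoints the plan prints neither an interval nor a comparison with the concurrent placebo arm. The Day 1 biopsy is used only to form a change score. At stake is how directly a report can state what rise in swellings, loss of IENFD or rate of absent wave V the data leave open.

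**Working it through.** **Inputs.** Sample size: "Approximately 60 adults 18 to 50 years of age will be randomized in a 1:1 allocation ratio" (SAP, Sample Size Determination), so 30 per arm, or about 40 if all the extra participants are added 1:1. The only SD in the plan is for latency: "Assuming a standard deviation of 0.2 ms", within a published range of 0.1 to 0.3 ms. No SD or correlation is given for IENFD or swellings, so biopsy precision is stated in units of the SD of change, and the correlation r is an assumption shown over a range.

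**1. The plan's own figure.** Per-arm half-width = 1.960 × 0.2 / √30 = 0.0716 ms, which reproduces the stated 0.07 ms. Over the published SD range it is 0.036 to 0.107 ms. It covers one arm and one endpoint; no such figure exists for the biopsies or wave V absence.

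**2. Biopsy precision without a covariate.** Per arm: t(29) / √30 = 0.37 SD of change. Arm difference: t(2n−2) × √(2/n).

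| Evaluable per arm | Half-width of difference (SD of change) |
|---|---|
| 40 | 0.45 |
| 30 | 0.52 |
| 27 (assumed 10% loss) | 0.55 |
| 24 (assumed 20% loss) | 0.58 |

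**3. Gain from using Day 1 as a covariate.** Assume equal variance σ² at baseline and follow-up. A change score has variance 2σ²(1−r), and ANCOVA has residual variance σ²(1−r²). The ratio is (1+r)/2, so interval width is multiplied by √((1+r)/2), ignoring the one degree of freedom spent and any chance baseline imbalance.

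| Assumed r | Width ratio | Narrower by | Half-width at 30 per arm (0.517 × ratio) |
|---|---|---|---|
| 0.3 | 0.806 | 19% | 0.42 SD of change |
| 0.5 | 0.866 | 13% | 0.45 |
| 0.7 | 0.922 | 8% | 0.48 |
| 0.9 | 0.975 | 2-3% | 0.50 |

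**4. Absence of wave V, hypothetical counts.**
- Clopper-Pearson upper limit for 0/30: 1 − 0.025^(1/30) = 11.6%. For 0/24 it is 14.2%, and for 0/40 it is 8.8%.
- 1/30 gives 0.1% to 17.2%; 2/30 gives 0.8% to 22.1%.
- Chan-Zhang difference at 30 per arm: 0 versus 0 gives about −12 to +12 percentage points; 2 versus 0 gives about −5.5 to +22.1.

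**The case against.** A reader might infer that these endpoints have no stated uncertainty. The documents do not support that. SAP 5.2 promises n, mean and SD or standard error, and SAP 8.1 shows the arms side by side, so an unadjusted interval per arm or for the difference is simple arithmetic. Wave V counts likewise determine their exact intervals, as the working shows.

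A reader might also infer that the whole nerve-toxicity question lacks intervals. It does not: the primary endpoint and wave V amplitude have baseline-adjusted models with 95% intervals.

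Other points against the concern stand in part:
- **No contradiction.** The statement that analyses focus on estimation (Protocol 9.1, SAP 5.1) sits in a paragraph that opens with the primary endpoint. It does not clearly reach these tables. Descriptive reporting here is consistent across both documents.
- **The missing contrast is not special.** SAP 6.1 states no arm difference for the primary endpoint either.
- **Baseline is not ignored.** Both biopsy endpoints are change scores. Normal BAEP is required at entry (Protocol 5.1), so there may be little baseline wave V absence to adjust for. What is missing is a baseline covariate. Age-and-gender normalisation of IENFD does not supply it, because it does not use the participant's own Day 1 value.
- **The extra participants are not a precision target.** Adding them depends on problems with sample integrity.
- **Skew and multiplicity.** Swelling percentages may be skewed, which is a fair reason to keep medians and ranges. Wave V tables are split by ear, intensity and visit. If 3 to 5 intensity steps are assumed, TP1 gives 2 ears × 2 visits × 3 to 5 steps = 12 to 20 difference intervals, to be read as description only.
- **Timing.** SAP Table 1 shows version 4.0 (17 Aug 2022) already describing analyses as added to the PCD CSR, and the current version is 5.0 (04 April 2023). Any new Month 9 contrast would follow that report, and Protocol 6.3.1 has sponsor staff unblinded after the PCD.

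**Conclusion.** The point holds in a limited form. For the two biopsy endpoints and absence of wave V, the SAP plans no interval, no baseline covariate and no between-arm estimate, while already using suitable methods elsewhere. The cost is lost precision and a less direct report. Unadjusted change scores in a randomised comparison are not biased, and the uncertainty can be recovered from the tables.

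The precision gain is modest: 19% at r = 0.3, falling to about 2-3% at r = 0.9. It rests on assumed correlations and equal variances, because the documents give no biopsy variability. The gain in clarity is greatest for wave V, where a printed 0% in 30 participants would still be compatible with a true rate of up to 11.6%. This is a cheap improvement to reporting, and no planned conclusion is invalid without it.

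**What to change.** - **SAP 6.2.2 and 6.2.3, Month 9/EOP:** add ANCOVA of change with the Day 1 value and treatment as terms. Report adjusted means and the ritlecitinib-minus-placebo difference, each with a 95% interval, beside the existing descriptives. Keep the median and range in view because of possible skew.
- **SAP 6.2.2 and 6.2.3, Month 15E:** add the 95% interval of the mean change in each group. Both groups are on active drug by then, so no placebo contrast is needed.
- **SAP 6.2.5:** add Clopper-Pearson 95% intervals per arm and, for TP1, the Chan-Zhang interval of the difference, by ear and intensity.
- **Status:** state that no hypothesis tests are attached. Label the Month 9 additions post hoc, since the PCD CSR preceded this SAP version.

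The cost is a few sentences of SAP text and a little programming. No new data are needed. The exact methods are already in the SAP, and the ANCOVA is a single-visit form of its baseline-adjusted model. The trade-offs are the post hoc label and a longer wave V table.

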### **6.2.3. IENFD in Skin Punch Biopsies**

- Endpoint: Change from baseline in IENFD in skin punch biopsies at Month 9/EOP and Month 15E.
- Population: Safety.
- Statistical Method: Descriptive statistics for continuous variables. Descriptive Summary of absolute and change from baseline in IENFD normalized by age and gender will also be provided.
  - For each participant normalized IEFND data was obtained by dividing the IEFND by the value of the LLN of each age range and gender, and multiplying it by 100 to obtain percentages. LLN is given by the 5th percentile of the distribution of IENFD by gender and age: females in age ranges of 18-39, 40-59 and 60+ are 8.0, 5.4 and 3.5 respectively, and for males, 5.9, 4.6 and 3.3 respectively.

### **6.2.4. Amplitude of Wave V on BAEP**

- Endpoint: Change and percent change from baseline in amplitude of wave V on BAEP at a stimulus intensity of 80dB at Months 6, 9, 9E, and 15E.
- Population: Safety.

- **Statistical Method:** For change from baseline, a linear mixed-effects model for Months 6 and 9 in [Section 5.2](#) will be used. The estimated means, with standard errors and 95% confidence intervals for each treatment group based on the model will be presented. Descriptive statistics based on observed data will also be provided. Descriptive statistics will be presented for data in the active therapy extension phase. Data from right side and left side will be summarized separately. For percent change from baseline, descriptive statistics will be presented.

#### **6.2.5. Absence of Wave V on BAEP**

- **Summary:** Proportion of subjects with an absence of wave V on BAEP at stimulus intensities ranging from 80dB to 40dB at Months 6, 9, 9E, and 15E.
- **Population:** Safety.
- **Statistical Method:** Descriptive statistics with number and percentage of subjects with the events only. Data from right side and left side will be summarized separately.

#### **6.2.6. Incidence of Treatment-emergent Adverse Events (TEAEs)**

- **Endpoint:** Incidence of subjects with treatment emergent adverse events.
- **Population:** Safety.
- **Statistical Method:** Descriptive statistics with number and percentage of subjects with the events only.

#### **6.2.7. Incidence of Treatment-emergent Serious Adverse Events (TESAEs)**

- **Endpoint:** Incidence of Treatment-emergent serious adverse events.
- **Population:** Safety.
- **Statistical Method:** Descriptive statistics with number and percentage of subjects with the events only.

#### **6.2.8. Incidence of Adverse Events (AEs) Leading to Discontinuation**

- **Endpoint:** Incidence of Adverse events (AEs) leading to discontinuation.
- **Population:** Safety.
- **Statistical Method:** Descriptive statistics with number and percentage of subjects with the events only.

#### **6.2.9. Incidence of Clinically Significant Abnormalities in ECG (only QTcF) and Vital Signs**

- **Endpoint:** Incidence of clinically significant abnormalities in ECG (only QTcF) and vital signs.

- Population: Safety.
- Statistical Method: Descriptive statistics with number and percentage of subjects with the events only.

#### **6.2.10. Incidence of Clinically Significant Abnormalities in Clinical Laboratory Values**

- Endpoint: Incidence of clinically significant abnormalities in clinical laboratory values.
- Population: Safety.
- Statistical Method: Descriptive statistics with number and percentage of subjects with the events only.

### **6.3. Secondary and exploratory Endpoints-Efficacy**

#### **6.3.1. Overall and AA SALT Scores**

- Endpoint: Change from baseline in overall and AA SALT scores in all the timepoints collected.

The AA SALT score at each visit will be calculated using non-AA SALT scores as follows:

- the non-AA SALT score collected at Month 9 (or Month 6) or the Early Termination visit (as appropriate) will be used for visits in TP1.
  - the non-AA SALT score collected at Month 15E or the Early Termination visit (as appropriate) will be used for visits in TP2, and
  - the non-AA SALT score collected at Month 51E or the Early Termination visit (as appropriate) will be used for visits in TP3.
  - The formula for deriving the AA SALT score is given by: AA SALT score = overall SALT score - non-AA SALT score.
  - non-AA scores that were blank will be considered as zero in cases there was no medical history indicating AGA
- Population: Efficacy.
  - Statistical Method: For placebo-controlled phase, a linear mixed-effects model in [Section 5.2](#) will be used. The estimated mean, standard errors and 95% confidence intervals for each treatment group, and mean difference with 95% confidence interval will be presented at each time point. Descriptive statistics will be presented for data in TP2 and TP3.

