5.1. Inclusion Criteria

Participants are eligible to be included in the study only if all of the following criteria apply:

Type of Participant and Disease Characteristics

1. Participants must meet the following AA criteria:

- Have a clinical diagnosis of AA. Other etiologies of hair loss coexistent with AA are allowed.
- $\geq 25\%$ scalp hair loss due to AA (including AT and AU) measured by SALT at screening which, in the opinion of the investigator, is appropriate for systemic therapy.
- Hair loss must be carefully reviewed to verify that $\geq 25\%$ terminal scalp hair loss is due to AA (ie, SALT [AA] score is ≥ 25). If in cases of concomitant AA and other etiologies of alopecia, it cannot be verified that SALT (AA) score is ≥ 25 , then the participant must be excluded from the study.

Hearing and Neurological Assessments at Screening

2. Participants must have normal hearing and BAEP assessed by the audiology professional and confirmed by the central reader.
3. Participants must have a normal neurological examination by a neurologist and absence of peripheral neuropathy by history, symptoms, and the neuropathy assessment. Participants with stable unilateral carpal tunnel syndrome or stable unilateral ulnar entrapment on neurological examination or history are allowed in the study.

Age

4. All participants must be 18 to 50 years of age at the time they sign the informed consent.

Sex

5. Male or Female

Contraceptive use by men or women should be consistent with local regulations regarding the methods of contraception for those participating in clinical studies.

The study protocol requirements regarding contraception are as follows:

- a. Male participants:
No contraceptive measures required.
- b. Female participants:
 - A female participant is eligible to participate if she is not pregnant or breastfeeding, and at least one of the following conditions applies:
 - Is not a woman of childbearing potential (WOCBP), See Section 10.4.

OR

- Is a WOCBP and using a contraceptive method that is highly effective, with a failure rate of <1%, as described in Section 10.4 during the intervention period and for at least 28 days after the last dose of study intervention. The investigator should evaluate the effectiveness of the contraceptive method in relationship to the first dose of study intervention.

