- 6. Any history of peripheral neuropathy (PN), including diabetic PN, chemotherapy-induced PN, drug-induced PN, genetic PN, idiopathic PN, etc.
- 7. Cognitive or behavioral conditions which could prevent the participant from cooperating with the investigator or audiology/neurology professionals performing the evaluations or procedures.
- 8. HbA1c $\geq 7.5\%$ at screening.
- 9. Current or recent history of clinically significant severe, progressive, or uncontrolled renal (including but not limited to active renal disease or recent kidney stones), hepatic, hematological, gastrointestinal, metabolic, endocrine (particularly thyroid disease and parathyroid disease, which can be associated with hair loss), pulmonary, cardiovascular, psychiatric, immunologic (other than AA), rheumatologic, dermatologic or neurologic disease; or have any other severe acute or chronic medical or psychiatric condition or laboratory abnormality that may increase the risk associated with study participation or study intervention administration, or interfere with the interpretation of study results; or in the opinion of the investigator or Pfizer (or designee), the participant is inappropriate for entry into this study, or

- unwilling/unable to comply with study procedures ([Section 8](#)) and Lifestyle Considerations ([Section 5.3](#)).
10. Any present malignancies or history of malignancies with the exception of adequately treated or excised non-metastatic basal cell or squamous cell cancer of the skin or cervical carcinoma in situ.
 11. History of any lymphoproliferative disorder such as Epstein Barr virus (EBV) related lymphoproliferative disorder, history of lymphoma, history of leukemia, or signs and symptoms suggestive of current lymphatic or lymphoid disease.
 12. History of disseminated herpes zoster or disseminated herpes simplex, or recurrent (more than one episode of) localized, dermatomal herpes zoster.
 13. History of systemic infection requiring hospitalization, parenteral antimicrobial therapy, or as otherwise judged clinically significant by the investigator within 6 months prior to Day 1 (for criteria regarding Tuberculosis [TB] infection, see Exclusion Criterion [21](#)).
 14. Known immunodeficiency disorder or a first-degree relative with a hereditary immunodeficiency.
 15. History of human immunodeficiency virus (HIV) or positive serology for HIV) at screening.
 16. Significant trauma or major surgery within 1 month of the first dose of study intervention.

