8.1.2. Clinical Assessments

8.1.2.1. Severity of Alopecia Tool (SALT)

SALT is a quantitative assessment of AA severity based on scalp terminal hair loss.⁽⁵²⁾ Scalp hair loss due to AA (AA SALT score) is measured at screening. The overall SALT score, which does not distinguish the reason for hair loss, will be collected at visits shown in the SoA (Section 1.3).

Score parameters utilize a visual aid showing the division of the scalp hair into four quadrants (back, top of scalp, and both sides), with each of the four quadrants given an accurate determination of the % of scalp surface area covered, representing 24%, 40%, 18%, and 18% of the total scalp surface area, respectively.

Hair prosthetics (eg, wigs, hair extensions) must be removed for clinical assessments of AA at all study visits.

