8.1.2.1.1. Non-AA SALT Score

In addition to the overall amount of scalp terminal hair loss, scalp hair loss due to etiologies other than AA will be assessed using the SALT tool. This will only be collected for participants known to have scalp hair loss due to other etiologies in addition to AA. The non-AA SALT score will be collected at visits shown in the SoA (Section 1.3).

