9.4.2. Efficacy Analyses

Efficacy data will be summarized by the treatment assignment based on efficacy population. The baseline is defined as the last measurement before the first dose in the placebo-controlled phase.

The secondary endpoints for SALT include both the overall SALT and AA SALT scores. The overall SALT score includes hair loss regardless of etiology (ie, scalp hair loss due to both non-AA and AA). The non-AA SALT score only takes into account scalp hair loss other than that due to AA and is required to be assessed only at:

- Month 9 (end of TP1) (or Month 6 for those participants, who enter the active therapy extension phase at Month 6),
- Month 15E (end of TP2) or Early Termination visit (as appropriate), and
- Month 51E (end of TP3) or Early Termination visit (as appropriate).

The AA SALT score at each visit will be calculated using non-AA SALT scores as follows:

- the non-AA SALT score collected at Month 9 (or Month 6) or the Early Termination visit (as appropriate) will be used for visits in TP1.

- the non-AA SALT score collected at Month 15E or the Early Termination visit (as appropriate) will be used for visits in TP2, and
- the non-AA SALT score collected at Month 51E or the Early Termination visit (as appropriate) will be used for visits in TP3.
- The formula for deriving the AA SALT score is given by: AA SALT score = overall SALT score – non-AA SALT score.

PCD CSR (Month 9; TP1)	
Endpoint	Statistical Analysis Methods
Primary	
 • There are no primary efficacy endpoints.
Secondary	
 • For PGI-C response, for the placebo-controlled phase, number and percentage with 95% confidence interval (based on Clopper-Pearson method) by treatment group, and treatment difference with 95% confidence interval (based on Chan and Zhang's exact method⁽⁵⁶⁾) will be presented. Participants who discontinue from the study for any reason or who switch to active therapy extension phase before Month 9 will be considered as non-responders. • In the placebo-controlled phase, change from baseline in overall and AA SALT score will be analyzed using linear mixed-effects model with baseline, treatment group, visit and treatment group by visit interaction as fixed effects, and participant as a random effect with unstructured covariance matrix assumption. The estimated mean, mean difference, with 95% confidence interval based on the model will be presented at each time point.

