### 3.5. Baseline Variables

Baseline values will be defined as follows for both safety and efficacy endpoints:

- Baseline is defined as the last non-missing measurement obtained before the first dose in the placebo-controlled phase.

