### 5.3. Methods to Manage Missing Data

- For the PCD CSR
  - For change from baseline in I-V interwave latency on BAEP, change from baseline in amplitude of wave V, and change from baseline in overall and AA SALT score during the placebo-controlled phase, the missing values will be handled in a linear mixed-effects model (Section 5.2).
  - For the PGIC response, participants who discontinue from the study for any reason or who switch to active therapy extension phase before Month 9 will be considered as non-responders at Month 9.
- For supplemental CSR 1 and CSR 2
  - All efficacy data will be summarized based on observed data. Missing data will not be imputed.

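### The SAP sets a blank non-AA SALT score to zero unless AGA is in the history, although the score covers hair loss of any cause other than AA; known non-AGA loss can then be counted as AA loss for a whole treatment period

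*SAP*

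**What the plan says.** Protocol 5.1 admits participants with mixed hair loss: "Other etiologies of hair loss coexistent with AA are allowed". For them the protocol adds a rating of the part not due to AA. Protocol 8.1.2.1.1 says who has it: "This will only be collected for participants known to have scalp hair loss due to other etiologies in addition to AA". Protocol 9.4.2 says what it covers: "The non-AA SALT score only takes into account scalp hair loss other than that due to AA". Neither section limits the cause.

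The score is rated once per period: at Month 9 (or Month 6 for early switchers), Month 15E and Month 51E, or at early termination. Protocol 9.4.2 and SAP 6.3.1 apply that one score to all visits of its period and subtract it from overall SALT to obtain AA SALT.

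SAP 6.3.1 alone adds a rule for blanks: "non-AA scores that were blank will be considered as zero in cases there was no medical history indicating AGA". AGA is expanded in neither document; I take it to mean androgenetic alopecia. The SAP does not say what happens to a blank score when AGA is in the history.

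**The concern.** The collection rule is triggered by any known non-AA cause, and the zero rule is switched off only by AGA. A participant with a known cause other than AGA falls between them: a rating is due, and if it is blank the SAP records no non-AA loss.

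The protocol itself points to causes other than AGA. Exclusion criterion 9 singles out endocrine conditions, "particularly thyroid disease and parathyroid disease, which can be associated with hair loss", but excludes only clinically significant disease that is severe, progressive or uncontrolled.

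AA SALT exists to isolate hair loss due to AA. It is a named secondary endpoint in TP1 and TP2 and exploratory in TP3. Because one rating feeds a whole period, one blank affects every visit of that period. Blanks in such participants are possible: Protocol 7.2 accepts incomplete early-termination procedures, and Protocol 10.9.2 and 10.9.8 restrict SALT to on-site visits. The AGA condition also suggests that the authors foresaw blanks in participants with known non-AA loss, since otherwise it would not be needed.

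**Working it through.** The plan gives no figure that depends on this rule, so there is none to reproduce. The check applies the SAP 6.3.1 formula.

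**Inputs from the documents.** AA SALT = overall SALT − non-AA SALT, with one non-AA score per period (SAP 6.3.1). About 30 participants per arm, about 60 in all (Protocol 9.2). TP3 is summarised as a single group (SAP 8.3).

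**Assumed inputs.** N, the true non-AA loss, is stable: 5 to 20 points. k, the number affected in a group, is 1 to 3. The documents give neither.

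**Step 1, level of AA SALT.** True value: O − N. Under the zero rule: O − 0. The error is +N at each visit of the period.

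**Step 2, change from baseline.** Let b = 1 if the score used for a period was blank and set to zero, and 0 if it was rated. Let b0 be the same for baseline, with b0 = 0 if baseline is the screening AA rating.

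- Derived change: [O − N(1 − b)] − [O_base − N(1 − b0)]
- True change: O − O_base
- Error: N(b − b0)

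**Step 3, example.** Assume overall SALT of 60 at screening and Day 1, then 55, 48 and 40 at Months 3, 6 and 9; N = 10, not AGA; Month 9 non-AA rating blank.

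| | Month 3 | Month 6 | Month 9 |
|---|---|---|---|
| AA SALT, true | 45 | 38 | 30 |
| AA SALT, zero rule | 55 | 48 | 40 |
| Change, true (baseline 50) | −5 | −12 | −20 |
| Change, zero rule, screening AA baseline 50 | +5 | −2 | −10 |
| Change, zero rule, baseline 60 with the same zero | −5 | −12 | −20 |

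**Step 4, across periods.** If baseline takes the TP1 zero (b0 = 1) and TP2 is rated (b = 0), the error is −10, a false improvement. If TP1 is rated and supplies the baseline (b0 = 0) and TP2 is blank (b = 1), the error is +10, a false worsening. With the screening AA baseline, a blank TP1 followed by a rated TP2 produces a fall of 10 points between Month 9 and Month 3E on top of any real change.

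**Step 5, which baseline applies.** Protocol 8.1.2.1 supports the screening rating: "Scalp hair loss due to AA (AA SALT score) is measured at screening". No non-AA rating is scheduled at screening or Day 1. Against that, Protocol 8.1.2.1.2 gives the screening AA rating the purpose of verifying eligibility, overall SALT is rated again on Day 1, and SAP 3.5 says "Baseline is defined as the last non-missing measurement obtained before the first dose in the placebo-controlled phase". Day 1 overall SALT minus the TP1 non-AA score is therefore also a possible reading. The documents do not settle it.

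**Step 6, group means, where the error enters.** Shift per arm = k × N/30:

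- k = 1, N = 5: 5/30 = 0.17
- k = 1, N = 10: 10/30 = 0.33
- k = 3, N = 10: 30/30 = 1.0
- k = 3, N = 20: 60/30 = 2.0

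TP3 single group, if all 60 contribute, k × N/60: 10/60 = 0.17 (k = 1, N = 10) to 60/60 = 1.0 (k = 3, N = 20). Fewer participants in TP3 would make the shift proportionally larger.

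**The case against.** The strongest objection is that the endpoint is a change, and the change may not be affected. If baseline AA SALT is derived with the TP1 non-AA score, the same zero sits in baseline and in every TP1 visit, and the TP1 error is exactly zero. This stands as a limit on the claim. It does not rescue the rule: AA SALT levels remain wrong, and step 4 shows that cancellation fails when periods differ in whether they were rated.

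Second, two things must coincide: known non-AGA loss and an omitted rating that the protocol requires. Protocol 10.9 asks for missed procedures at the next opportunity, and 10.9.4 gives the Month 9 visit up to 60 extra days. This also stands. The documents show that such a blank is possible, not that one occurred.

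Third, the size is small against the noise. With an assumed residual SD of 20, the 95% half-width for a difference between two arms of 30 is 1.96 × 20 × √(2/30) = 10.1 points. One affected participant with N = 10 shifts one arm by 0.33, about 3% of that; the extreme of 2.0 is about 20%, and only if all affected participants are in one arm. With equal numbers in both arms the difference does not move, although both means do.

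A reader might infer that the rule contradicts SAP 5.3 outright, since for the supplemental reports that section says "All efficacy data will be summarized based on observed data. Missing data will not be imputed". It does so only where a rating was due. Where no non-AA loss is known, no rating was due and zero is the right value.

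**Conclusion.** The rule is wrong as written: its trigger is narrower than the score it fills in. In an affected participant AA SALT is too high by the full non-AA loss at every visit of the period where overall SALT was rated. That part follows from the formula alone.

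A reader might go further and conclude that the treatment comparison on AA SALT in TP1 is biased. The documents do not support that. It requires the screening AA rating as baseline, at least one affected participant, and an uneven split between arms; the SAP does not fix the first, and the documents show neither of the others. The shifts of 0.17 to 2.0 points per arm, and 0.17 to 1.0 in the TP3 group, are illustrations on assumed k and N.

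The number affected may be zero. The endpoint is secondary or exploratory and serves estimation only. The primary BAEP endpoint, overall SALT and the stated precision figure do not change. The point merits a correction because the rule is clearly inconsistent with the protocol and cheap to put right.

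**What to change.** In SAP 6.3.1, replace the condition on AGA history with *no known scalp hair loss of any non-AA aetiology (medical history or investigator record)*. State that a blank score in any other participant, including one with AGA, is missing, so that AA SALT for that period is missing and SAP 5.3 applies. In the same paragraph, expand AGA if the term is kept and name the source of baseline AA SALT.

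A difference between overall and AA SALT at screening is useful as a prompt to query the site. It should not be a condition in the rule: these are two visual ratings, and a requirement of exact equality could void AA SALT for a whole period in participants with no known non-AA cause.

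The cost is a few sentences and a check of the participants with a blank score; no new assessment is needed. Affected participants lose AA SALT for the period and keep overall SALT. The SAP version history refers to the primary-completion report as already prepared, so any TP1 value that changes must be labelled as specified after primary completion.
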